The Durata® family of ICD leads utilizes a silicone polyurethane co-polymer insulation known as Optim which has been associated with a significant reduction in abrasion when compared to Riata and Riata ST silicone insulated leads. Although the incidence of these insulation abrasion issues is extremely low in Durata leads, the Durata leads are being included in this study for comprehensive

analysis across all St. Jude Medical ICD lead types. This study aims to prospectively determine the prevalence and incidence of lead compromise evidenced by imaging (includes externalized conductors and other visual lead anomalies, by each subcategory, as listed in Appendix A) and electrical dysfunction in patients with Riata, Riata ST silicone ICD, QuickSite/QuickFlex CRT and Durata ICD leads. Prevalence as well as incidence of externalized conductors and other visual lead anomalies will be separately analyzed and reported. In addition, this study will provide information to the physicians regarding the possibility that an observation of externalized conductors with normal electrical function may progress to an electrical malfunction. The SJM Cardiac Lead Assessment Study is sponsored by St. Jude Medical (SJM) and constitutes the modification of the “Riata Lead Evaluation Study”.

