3.0 Clinical Protocol

3.1 Study Design and Scope

This study is a prospective, non-randomized, multi-center, international post market study that will determine the prevalence and incidence of externalized conductors and other visual lead anomalies (as evidenced by imaging) and the risk of progression to electrical dysfunction in a large series of ICD/ CRT-D/CRT-P devices containing one or more of the following SJM leads: Riata leads, Riata ST silicone leads, Durata leads, QuickSite/QuickFlex CRT leads. A patient that has at least one market released lead implanted in time period indicated in Table 1 is eligible for enrollment in the study. Each lead group will be considered separately for independent analysis.

Table 1: Leads Eligible for Enrollment

Lead Group	Model Numbers	Lead Implant Date
Riata	1560, 1561, 1562, 1570, 1571, 1572, 1580, 1581, 1582, 1590, 1591, 1592	2002-2009
Riata ST Silicone	7000, 7001, 7002, 7010, 7011, 7040, 7041, 7042	2006-2009
QuickSite/QuickFlex	1056T, 1058T, 1156T, 1158T	2006-2010
Durata	7120, 7121, 7122, 7130, 7131, 7120Q, 7121Q, 7122Q, 7170Q, 7171Q, 7172Q	2008-2010

In order to determine the prevalence and incidence of externalized conductors, other visual lead anomalies as well as electrical dysfunction in the population of leads being evaluated, a minimum of 1500 leads listed above will be enrolled at up to 60 sites. This will comprise a minimum of 300 leads in the Riata lead group and a minimum of 200 leads in the Riata ST lead group to make a combined total of at least 500 Riata and Riata ST silicone leads. The study will also include at least 500 leads in the QuickSite/QuickFlex and Durata lead groups. All patients will be followed every six months for three years.

Adequate representation across the different ages of the leads is also needed to understand the lead population being studied. Therefore, the leads from each group of leads will be compromised of subgroups based on the age of lead (at enrollment) being studied. The required minimum enrollment for each subgroup per lead group is indicated in Table 2. Even if the minimum enrollments indicated in Table 2 are met, extra enrollments may be required to ensure a minimum of 500 leads in each lead group.

Expected Attrition in patients with high voltage leads

Withdrawals due to death

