For QuickSite/QuickFlex leads only, data from patients with an additional 1 year of follow-up will contribute to 2 separate lead subgroups (See Section 3.4.5).

3.2.2.6 Adverse Event rate through 30 days post-intervention for lead (e.g. extraction, abandonment, revision, other)**Lead Population**

All the leads within the Riata, Riata ST silicone, QuickSite/QuickFlex (1056T, 1058T, 1156T, 1158) and

Durata lead subgroups that require an intervention/revision (e.g. extraction, abandonment, other)

Analysis

The 30-day adverse event rate will be calculated as the number of adverse events within 30 days associated with study lead related interventions in each of the 4 lead groups divided by total study lead related interventions in each of the 4 lead groups.

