3.2.2.8 Time from other visual lead anomalies by each subcategory to clinical intervention

Lead Population

All the leads with other visual lead anomalies (by each sub category) within the Riata, Riata ST silicone, QuickSite/QuickFlex (1056T, 1058T, 1156T, 1158), and Durata lead groups

Analysis:

Time to clinical intervention will be analyzed using the Kaplan-Meier method. The zero time will be the date at

which other visual lead anomaly (by each subcategory) was detected. Those patients who experience other visual lead anomaly (by each subcategory) after enrollment but do not experience clinical intervention will be censored 3 years after enrollment in this trial. A separate Kaplan-Meier curve will be calculated for each of the lead subgroups outlined in Table 2.

For QuickSite/QuickFlex leads only, data from patients with an additional 1 year of follow-up will contribute to 2 separate lead subgroups (See Section 3.4.5).

3.2.2.9 Comparison of patients with lead compromise as evidenced by imaging (includes externalized conductors and other visual lead anomalies by each subcategory) to those without lead compromise

Patient Population

All the patients within the Riata, Riata ST silicone, QuickSite/QuickFlex (1056T, 1058T, 1156T, 1158) and Durata lead subgroups.

Analysis

Demographic and clinical parameters will be compared between patients who experience a lead compromise as evidenced by imaging and those who do not experience a lead compromise. Specifically, the variables age, gender, body mass index, lead size, lead model, and implant factors such as venous access site, number of other leads in the vasculature, fixation location in the right ventricle, level of activity (based on functional NYHA class scale I, II, III, IV), level of therapy that patient received (no ATP/shock, ATP or shock) and slack (grades 0, 1, 2, 3, 4 based on the scale described by Ha et al., 2010¹²) in the lead will be used for the comparison. Continuous variables such as age or body mass index will be compared using Student's T-tests while categorical variables such as gender or lead models will be compared using Pearson's Chi-square statistic. Point estimates and p-values will be provided from these analyses.

3.2.2.10 Comparison of patients with electrical dysfunction to those without electrical dysfunction.

Patient Population

All the patients within the Riata, Riata ST silicone, QuickSite/QuickFlex (1056T, 1058T, 1156T, 1158) and Durata lead subgroups.

Analysis

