Demographic and clinical parameters will be compared between patients who experience electrical dysfunction and those who do not experience electrical dysfunction. Specifically, the variables age, gender body mass index, lead size, lead model, and implant factors such as venous access site, number of other leads in the vasculature, fixation location in the right ventricle, level of activity (based on functional NYHA class scale I, II, III, IV), level of therapy that patient received (no ATP/shock, ATP or shock) and slack in the lead (grades 0, 1, 2, 3, 4 based on the scale described by Ha et al, 2010¹²) will be used for the comparison. Continuous variables such as age or body mass index will be compared using Student's T-tests while categorical variables such as gender or lead models will be compared using Pearson's Chi-square statistic. Point estimates and p-values will be provided from these analyses.

In addition, the two patient groups will be compared for the following endpoints:

1. Frequency of externalized conductors. This will be done using a Pearson's Chi-square analysis.
2. Frequency of other visual lead anomalies. This will be done using a Pearson's Chi-square analysis.
3. Time to detection of externalized conductors. A Kaplan-Meier analysis will be used for this comparison.
4. Time to detection of other visual lead anomalies. A Kaplan-Meier analysis will be used for this comparison.
5. The extent of externalization will be compared using Pearson's Chi-square analysis.
6. Number of zones with externalization within one lead will be compared using a Student's T-test.
7. Location of externalization will be compared using Pearson's Chi-square analysis.
8. Amount of slack in the lead (based on the scale described by Ha et al, 2010)¹² will be compared using Pearson's Chi-square analysis.

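### Sections 3.2.2.9 and 3.2.2.10 do not carry through the rule that lead groups are analysed separately; read as written they pool four lead groups in unadjusted tests, which can create, mask or reverse an association

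*Combined protocol and SAP*

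**What the plan says.** Section 3.1 gives the general rule: "Each lead group will be considered separately for independent analysis". Most outcome measures repeat it in their analysis paragraph, either as a rate per lead group or as a separate hazard rate or Kaplan-Meier curve per Table 2 subgroup. Section 3.2.2.6, for example, uses a denominator "divided by total study lead related interventions in each of the 4 lead groups".

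The last two secondary measures do not. In both, the population is "All the patients within the Riata, Riata ST silicone, QuickSite/QuickFlex (1056T, 1058T, 1156T, 1158) and Durata lead subgroups". The contrast in 3.2.2.9 is: "Demographic and clinical parameters will be compared between patients who experience a lead compromise as evidenced by imaging and those who do not experience" one. Section 3.2.2.10 does the same for electrical dysfunction and then adds a list of eight endpoints: "In addition, the two patient groups will be compared for the following endpoints". The first of these is "Frequency of externalized conductors. This will be done using a Pearson's Chi-square analysis".

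Lead model is one of the variables compared singly: "categorical variables such as gender or lead models will be compared using Pearson's Chi-square statistic". It is not used as a stratum or covariate, and no adjustment is named.

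**The concern.** The four groups are silicone high-voltage leads (Riata, Riata ST), Optim-insulated high-voltage leads (Durata) and left ventricular leads (QuickSite/QuickFlex). The Introduction reports externalization from 0.5% to 33.3% depending on Riata/Riata ST model, and says of abrasion that "the incidence of these insulation abrasion issues is extremely low in Durata leads". Lead group is therefore expected to predict externalization.

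If lead group also predicts electrical dysfunction, it confounds endpoint 1 of 3.2.2.10. That endpoint bears on a stated aim of the study: whether externalization with normal electrical function may progress to malfunction. The same applies to any patient factor whose frequency differs between groups, NYHA class for instance.

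Two listed comparisons are also hard to interpret when high-voltage and left ventricular leads are mixed. Right-ventricular fixation location does not describe a left ventricular lead. Externalization location is coded in Regions 1-4 for high-voltage leads and a-d for CRT leads (Appendix A), so lead type is built into a pooled test of location.

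**Working it through.** The plan states no sample size, power or significance level for these comparisons, so there is no figure of its own to reproduce. The check asks how a pooled test behaves when externalization and dysfunction are independent inside every lead group.

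**Inputs from the documents**
- Target sizes, Table 2: Riata 195 + 185 + 180 = 560; Riata ST 185 + 180 = 365; together 925. QuickSite/QuickFlex 225 + 225 + 300 = 750. Durata 3 × 275 = 825. Total 2,500.
- Minimum sizes, Section 3.1: 300 Riata, 200 Riata ST, and 500 in each of the other two groups (read as 500 each, which matches the stated total of 1,500).

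**Assumptions**
- Two-sided 5% level, one lead per patient.
- Externalization 20% / 3% / 0.5% in Riata with Riata ST / QuickSite-QuickFlex / Durata.
- Dysfunction varied by scenario, since the documents give no rate for any group.

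**Pooled odds ratio from expected counts, dysfunction 6/3/1%, target sizes**
- Externalized and dysfunctional: 925×0.20×0.06 + 750×0.03×0.03 + 825×0.005×0.01 = 11.10 + 0.675 + 0.041 = 11.82.
- All externalized: 185 + 22.5 + 4.125 = 211.6, so externalized without dysfunction = 199.8.
- All dysfunctional: 55.5 + 22.5 + 8.25 = 86.25, so dysfunctional without externalization = 74.4.
- Neither: 2,500 − 211.6 − 74.4 = 2,213.9.
- Odds ratio = (11.82 × 2,213.9) / (199.8 × 74.4) = 1.76, although it is 1 in every group.

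**Rejection rates by simulation (at least 20,000 runs per scenario, no within-group link)**

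| Sizes | Dysfunction | Pooled odds ratio | Pooled test rejects |
|---|---|---|---|
| 925/750/825 | 6/3/1% | 1.76 | about 43% |
| 500/500/500 | 6/3/1% | 1.79 | about 31% |
| 925/750/825 | 3/2/1.5% | 1.35 | about 14% |
| 500/500/500 | 3/3/2% | 1.13 | about 6% |
| 925/750/825 | equal in all | 1.00 | about 5% |

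With dysfunction ordered the other way (1/3/6%, target sizes) the pooled odds ratio is 0.37, so pooling can also hide or reverse a real link.

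**Four groups kept apart at minimum sizes (300/200/500/500)**, with assumed externalization 25/10/3/0.5%:
- Dysfunction 4/4/2/2%: odds ratio 1.44, about 14% rejection.
- Dysfunction 5/4/2/1%: odds ratio 1.85, about 28%.
- Dysfunction equal at 4%: odds ratio 1.00, about 5%.
- A patient factor with no within-group effect on externalization, such as NYHA III/IV: at 60% in QuickSite/QuickFlex and 30% elsewhere, odds ratio 0.76 and about 27% rejection; at 50% against 35%, odds ratio 0.87 and about 10%.

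A Cochran-Mantel-Haenszel test stratified by lead group rejected in about 4% to 5% of runs in every scenario.

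**The case against.** The strongest reply is that pooling is never stated. Section 3.1 sets a study-wide rule and nothing later revokes it. The population line proves little, because 3.2.2.6 lists all four lead groups in similar words and is still analysed per group. Comparing lead models proves little either, since Table 1 lists several models within every group. The phrase about two patient groups could describe a comparison repeated in each lead group.

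This stands to the extent that a reader might infer a flat contradiction between 3.1 and the later sections, and the documents do not support that. They support an omission whose plain reading is a pooled test. Section 3.2.2.6 adds its split in the analysis paragraph; 3.2.2.9 and 3.2.2.10 do not. Two analysts could run different analyses from this text.

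A reader might also infer that a false link will appear. That needs dysfunction to differ between groups, and no dysfunction rates are given. Equality is not a safe default, though. Dysfunction counts only if the lead was capped, extracted or abandoned (Section 2.0), and Section 3.1 expects recalled Riata/Riata ST leads to be explanted more often.

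Far larger error rates, about 94%, can be obtained for a factor present in all QuickSite/QuickFlex patients and 40% of the others. Such a factor is in effect CRT status, which is not on the comparison list, so that figure should not be used.

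Right-ventricular fixation location is not wholly undefined for QuickSite/QuickFlex patients either: the comparison is by patient, and such a patient may also carry a Riata or Durata lead.

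Finally, these are secondary, single-variable comparisons with no decision rule, and all primary measures are split by lead group. That limits the consequence. Section 3.2.2.4 follows externalized leads by subgroup but has no comparator without externalization, so it does not replace endpoint 1.

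**Conclusion.** The concern holds as an unresolved analysis choice with a real but conditional risk of confounding. Under the plain reading, and with no within-group link, the pooled externalization-dysfunction test rejects falsely in anything from about 5% to about 43% of trials across the main scenarios. The upper value rests on assumed dysfunction of 6/3/1% and the Table 2 target sizes; the projected cumulative enrollment of 2,110 in Section 3.1.1 lies between those targets and the 1,500 minimum. The direction is not fixed.

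The documents support the expectation that externalization differs by lead model. The dysfunction rates, the patient-factor rates and the externalization rates chosen for each group are assumptions. The primary outcome measures are not affected. The change should be made because it is cheap and removes the problem whichever reading was intended.

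**What to change.** In 3.2.2.9 and 3.2.2.10:
- State that all comparisons are made within each lead group, with the lead as the unit of analysis. If the patient is kept as the unit, give a rule for patients who carry study leads from two groups; a stratified test needs each unit in one stratum.
- State that any overall result is stratified by lead group: Cochran-Mantel-Haenszel for categorical factors, and lead group as a model term for continuous ones.
- Analyse externalization location separately for high-voltage leads (Regions 1-4) and CRT leads (Regions a-d), and restrict right-ventricular fixation location to high-voltage leads.

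The cost is SAP wording and more tables, with no new data. Each within-group comparison will have fewer events and so less power, chiefly where events are rare. A stratified overall test recovers much of that.
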